Participants: We will enroll up to 60 older adults (age 50+), who are right handed and MRI compatible, from the VA Ann Arbor Healthcare System, the University of Michigan Alzheimer’s Disease Center (MADC), and the surrounding community. Enrollment is open to participants regardless of race, gender, or social status.

Inclusion criteria: Patients will receive a diagnosis of MCI based on the Albert et al. (2011) criteria. Specifically, patients will **1)** report a subjective decline in memory (report can also be provided by an informant), **2)** demonstrate objective impairment in memory (based on Neuropsychological testing), and **3)** remain independent in activities of daily living. All patients will be stable on nootropic medications for at least 1-2 months prior to study initiation.

By definition, healthy controls (HC) will be free of objective memory test impairment (i.e., all scores within normal limits on the standardized testing protocol below).

Exclusion criteria: A history of **1)** contributory other neurological (e.g., epilepsy, moderate - severe traumatic brain injury) or medical conditions that are known to affect cognitive functioning; **2)** significant psychiatric conditions (e.g., moderate - severe depression, bipolar disorder, schizophrenia); **3)** sensory impairments that limit the ability to take part in the study; **4)** a significant history or current use of alcohol or drug abuse/dependence. Participants will also be screened to ensure MRI compatibility (assessed using the guidelines set forth by the American College of Radiology); some of the criteria for which are also reasons for excluding someone from tDCS (e.g., metallic or electronic implants). Eligible participants who cannot undergo MRI will be enrolled in the study and will complete only the stimulation and behavioral portions of the study. We have successfully used this same approach in our previous RCTs.

Recruitment: Participants will be recruited from both the VA Ann Arbor Healthcare system and the University of Michigan Alzheimer’s Disease Center. The primary recruitment source of MCI patients at the VA will be the Neuropsychology Clinic while HC will be recruited from the general VA community via postings/flyers in approved areas. The primary recruitment site for non-Veterans will be the University of Michigan Alzheimer’s

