Disease Center (MADC). The MADDC recruits participants from several sources including its memory disorders clinic, community screening events, and external referrals. Participants interested in research are maintained in an IRB-approved database, which is available to the PI and his study team. This database includes individuals who are cognitively intact (HC) and those with MCI.

Screening & Cognitive Assessment: After providing informed, written consent, participants will undergo a brief neuropsychological protocol to ensure they continue meeting MCI criteria as outlined above (for patients) or that they are, in fact, cognitively intact (for the HC). This protocol includes standardized measures that are shown in the table below. Other measures may be added to the protocol to characterize the nature of the patient's cognitive functioning as necessary. Participants will be given breaks as necessary to ensure their comfort and are allowed to discontinue at any point for any reason.

Measure	Description	Screening Session
Montreal Cognitive Assessment (MOCA)	Gross screening measure for overall cognitive functioning (~5 minutes)	X
Wechsler Test of Adult Reading (WTAR)	Single word reading – used to establish premorbid intellectual estimates (~3 minutes)	X
Repeatable Battery for the Assessment of Neuropsychological Status (RBANS)	Brief Neuropsychological battery that includes Indices of attention, visuospatial, learning, memory, and processing speed. (~20 minutes)	X
Emory short version of Wisconsin Card Sorting Test (WCST)	Assesses the ability to identify possible solution strategies and abstract problem solving (~5-15 minutes)	X
Trail Making Test	Measures of psychomotor processing (Trails A) and set shifting (Trails B) (~3-10 minutes)	X
Temporal Sequencing Task	Novel Temporal Memory Task (~5 minutes)	X
Functional Activities Questionnaire (FAQ)	Evaluates patient's ability to perform everyday tasks (i.e., ADLs/IADLs) (~3 minutes)	X
Geriatric Depression Scale (GDS)	Evaluates current symptoms of depression (~3 minutes)	X
Multifactorial Memory Questionnaire (MMQ) & Memory Assessment Clinics – self report (MAC-S)	Self-report questionnaires that assess perceived memory complaints (~15minutes)	X
Object Location Touchscreen Test (OLTT)	Assesses the ability to learn and remember the location of objects (~10 minutes)	X
Screening protocol.		

Eligible participants move forward into the study, details of which are provided below.

Study Procedures:

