Eligible participants will undergo 2 sessions within a 2-week period of time. Some degree of flexibility is necessary with these visits in order to accommodate both patient and MRI availability.

Once determined to be eligible, participants will be randomized to one of two groups within their respective diagnostic groups. The first group will receive active HD-tDCS during session 1 and then sham HD-tDCS during session 2. The second group will receive the opposite order.

Participants will first receive 20 minutes of HD-tDCS at 2mA or sham as appropriate to the assigned condition. Participant specific codes are entered into the Soterix Medical Inc Clinical Trial unit thereby ensuring participants and study staff are blinded to stimulation condition. Stimulation will be performed using a Soterix Medical Inc. tDCS unit (Clinical Trial system with attached 4x1 HD stimulation unit) within a quiet room. The unit automatically discontinues stimulation after the specified time has elapsed (here 20 minutes). The patient will

complete a brief questionnaire about the nature and severity of any side effects (see tDCS Safety below) as well as whether they believe they received active or sham stimulation.

The active tDCS protocol will provide an initial ramp-up period in which the electrical current is gradually increased, followed by 20 minutes of stimulation at 2mA, and finally a ramp down period during which the electrical current is gradually removed.

The sham tDCS group will receive a ramp-up period to 2mA followed immediately by ramp down period. This is repeated at the end of the session.

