fMRI Scanning: After completing HD-tDCS, participants will be escorted to the MRI machine where they first undergo a resting-state fMRI scan and then complete the spatial navigation task. Structural imaging data were collected through a GE MR750 3T magnetic resonance system (GE, Milwaukee, WI) with a 32-channel phased array head coil. Sequence parameters for acquisition were: Field of view (FOV) = 256, Matrix = 256 × 256, 156 slices per volume, 1 mm³ voxel size, TR = 12 ms, TE = 5 ms, TI = 500 ms, flip angle = 15°. For resting state fMRI, participants were instructed to focus their gaze on the fixation cross on the screen and to not fall asleep. Resting state data was acquired through an echo planar imaging (EPI) multi-band sequence and parameters were: FOV = 240, Matrix = 74 × 74, 45 slices per volume, 3.4 × 3.4 × 3 mm voxel size, TR = 900 ms, TE = 30 ms, flip angle = 70°. For the functional task portion, participants were instructed to view the spacial navigation videos and remember key landmarks or series of turns depending whether it was allocentric or egocentric task. Functional task data was also acquired through an echo planar imaging (EPI) multi-band sequence with the following parameters: FOV = 220, Matrix = 88 × 88, 51 slices per volume, 2.5 × 2.5 × 2.5 mm voxel size, TR = 1200 ms, TE = 30 ms, flip angle = 70°.

Memory Testing: After scanning, participants perform a spatial navigation memory test that uses a touchscreen monitor to evaluate responding. Allocentric accuracy is measured as the distance (in CM) between the actual and selected location (lower values indicate greater accuracy) of a given landmark within a given map. Egocentric memory accuracy is evaluated by showing participants an image of a given environment after which they recall the sequence of turns through the environment. The dependent variable is the number of turns correctly recalled.

Statistical Design:

The primary analytic technique for the behavioral measures will be a repeated measures ANOVA (via the current version of SPSS). The effects of HD-tDCS for allocentric and egocentric performance will be examined separately. These analyses may include potential confounding factors as covariates.

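### The repeated measures ANOVA as named would normally drop anyone who stops after session 1; no other rule is given, and the active-sham estimate is modestly biased if stopping differs by order and depends on score

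*Combined protocol and SAP*

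**What the plan says.** Under Statistical Design: "The primary analytic technique for the behavioral measures will be a repeated measures ANOVA (via the current version of SPSS". Allocentric and egocentric scores are analysed separately, and "These analyses may include potential confounding factors as covariates". The SPSS procedure and the model terms are not named.

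Under Study Procedures: "Eligible participants will undergo 2 sessions within a 2-week period of time". Order is randomised within diagnostic group: "The first group will receive active HD-tDCS during session 1 and then sham HD-tDCS during session 2", and "The second group will receive the opposite order".

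Under Memory Testing: "After scanning, participants perform a spatial navigation memory test that uses a touchscreen monitor to evaluate responding". The behavioural outcome is thus obtained within a session, and a person who attends only session 1 has one usable score.

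The only text on discontinuation is in Screening & Cognitive Assessment, where participants "are allowed to discontinue at any point for any reason". The document has no analysis population, missing-data rule, expected dropout, replacement rule or sensitivity analysis. The provision for people who cannot have MRI deals with missing scans, not with a missing second session. The closing sentence that allows further analyses does not mention missing data.

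**The concern.** A standard repeated measures ANOVA works on complete pairs. With two sessions, one missed session removes the person from the behavioural analysis.

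In this design the deletion need not be neutral. What a person received in session 1 is fixed by randomised order. Suppose poor scorers are likelier to stop, and more people stop in one order than in the other. The completers in the two orders are then selected to different degrees. The session 1 score of completers is inflated by that selection more than their session 2 score, because the two scores are only partly correlated. Session 1 is active in one order and sham in the other, so the two distortions push the active-sham contrast in opposite directions. They cancel only if they are equal.

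At stake is whether the Aim 1 contrast remains the randomised comparison or becomes one among people who came back. Putting order in the ANOVA does not settle this, because the selection takes place within each order.

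**Working it through.** The plan gives no power calculation, SD, effect size or dropout rate, so there is no figure to reproduce. The check asks how large the bias could be under assumed stopping.

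**Inputs**
- From the plan: at most 60 participants, two sessions, two orders.
- Assumed: 30 per order; score SD 1, scaled so that higher is better (allocentric distance reversed); within-person correlation ρ = 0.5 (range 0.3 to 0.7); benefit τ = 0.3; practice gain π = 0.3; log-odds of stopping after session 1 rising by 1 per SD of poorer session 1 score; average stopping rate r set separately in each order.

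**Formulas**

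Let e be the session 1 deviation from its mean, standard normal, and let the probability of stopping be p with logit(p) = a − e. The mean of e among those who stay is

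m = E[p(1 − p)] / (1 − r),

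and their mean session 2 deviation is ρm. Among completers the expected active-minus-sham difference is

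- active first: τ − π + (1 − ρ)m_A
- sham first: τ + π − (1 − ρ)m_S

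Averaging the two orders equally, which is what including order achieves, gives

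bias = (1 − ρ)(m_A − m_S) / 2.

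The practice gain cancels and the selection term does not.

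**Values of m**, with a solved numerically for each r:

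| r | a | E[p(1−p)] | m |
|---|---|---|---|
| 5% | −3.37 | 0.0448 | 0.0448/0.95 = 0.0471 |
| 10% | −2.56 | 0.0817 | 0.0817/0.90 = 0.0908 |
| 20% | −1.65 | 0.1386 | 0.1386/0.80 = 0.1732 |
| 30% | −1.02 | 0.1770 | 0.1770/0.70 = 0.2528 |

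**Bias with order in the model, ρ = 0.5**

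| Stopping, active first / sham first | People lost | Bias (SD) |
|---|---|---|
| equal rates | – | 0 |
| 10% / 5% | 30 × 0.15 = 4.5 | 0.25 × (0.0908 − 0.0471) = 0.011 |
| 20% / 5% | 30 × 0.25 = 7.5 | 0.25 × (0.1732 − 0.0471) = 0.032 |
| 30% / 5% | 30 × 0.35 = 10.5 | 0.25 × (0.2528 − 0.0471) = 0.051 |

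Simulated trials of 60 under the same assumptions gave 0.030 to 0.031 for the 20%/5% row and 0.046 to 0.049 for the 30%/5% row. At 20%/5% the bias is 0.35 × 0.1261 = 0.044 for ρ = 0.3 and 0.15 × 0.1261 = 0.019 for ρ = 0.7. Against a simulated standard error of 0.137, the first two non-zero rows are 0.011/0.137 = 8% and 0.032/0.137 = 23% of one standard error.

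**Without order in the model, 20%/5%, ρ = 0.5.** Active-first completers carry weight 0.80/1.75 = 0.457 and sham-first completers 0.543. Selection contributes 0.5 × (0.457 × 0.1732 − 0.543 × 0.0471) = 0.027. Practice contributes 0.3 × (0.543 − 0.457) = 0.026. The total is about 0.053. Including order brings this down to 0.032; the difference of 0.021 comes from leaving order out, which is a separate matter.

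**A harsher pattern.** If the score drives stopping in the active-first order only (log-odds 1.5 per SD, 30% versus 10%), the order-adjusted bias is 0.116, 0.080 and 0.050 SD at ρ = 0.3, 0.5 and 0.7. Across the simulated patterns in which stopping depends on both order and score, with N = 60 and no true or session effect, the type I error of the unadjusted completers' test was 0.054 to 0.085.

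**Mixed model on all observed sessions.** With stimulation and session terms, its large-sample bias stayed within 0.005 SD in every pattern. With 15% random stopping and ρ = 0.5, the SD of the estimate was 0.139, against 0.140 for completers only; another run put the gain at about 2%.

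**The case against.** The strongest reply is that the condition behind the bias has no source in the document. The tDCS Safety section describes side effects as mild and about equally frequent under active and sham. Study Procedures blinds participants and staff, and sham ramps to 2 mA at both the start and the end of the session. There are only two visits, within two weeks. The plan does not say that participants learn their memory score. All of this points away from a fourfold difference in stopping between orders. With equal rates the bias is nil, and at 10% versus 5% it is about 0.01 SD. This stands, and it makes the point conditional and small.

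A reader might infer more in four ways, none of which the document supports:
- **That the benefit will be overstated by about a sixth** (0.053/0.3 = 17.5%). That figure needs assumed 20% versus 5% stopping, and part of it is practice gain, which an order term removes. The part that remains is 0.0315/0.3 = 10.5%, on the same assumed rates.
- **That the permission to discontinue forecasts withdrawal between sessions.** It stands in the screening section, beside the offer of breaks during testing.
- **That valuable information is thrown away.** Lone session 1 scores add almost no precision.
- **That deletion is a stated rule.** The SPSS procedure is not named. Deletion is what the named method does by default, and nothing in the plan overrides it.

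What the reply leaves untouched is that the named method normally requires both sessions, that no rule for incomplete pairs exists, and that the plan nowhere assumes full retention.

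**Conclusion.** The point holds in a conditional form. As written, the primary behavioural analysis would by default omit anyone with only session 1. If stopping differs by order and also depends on the session 1 score, the estimate is biased even with order in the model: about 0.01, 0.03 and 0.05 SD at 10%, 20% and 30% stopping after active first, against 5% after sham first. These sizes rest on assumed values for stopping, correlation and score dependence, none of which the plan gives.

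The direction is not fixed either. Swapping the rates between orders reverses the sign. If one score-based rule applies in both orders and active stimulation truly helps, slightly fewer people stop after active, and the estimate moves toward no effect. In one simulated case (benefit 0.4 SD, no session effect, ρ = 0.5, 8.1% versus 12.7% stopping) the order-adjusted shift was 0.010 SD.

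This is a modest weakness. It is worth correcting because a better method is available in the same software at almost no cost.

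**What to change.** Make the primary analysis of the behavioural outcomes a likelihood-based mixed model (SPSS MIXED, REML, small-sample degrees of freedom such as Kenward-Roger or Satterthwaite). Use stimulation, session, diagnostic group and stimulation-by-group as fixed effects and participant as a random effect. Include every randomised participant with at least one tested session, by assigned condition. For the egocentric outcome, a count of turns, check the normal approximation or use the generalised mixed-model equivalent. Report the number and reasons for stopping after session 1 by order, and keep the completers-only ANOVA as a sensitivity analysis.

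The cost is a change of wording, with the same data and software and no material loss of precision. The model assumes that stopping depends only on observed data (order and session 1 score) and that there is no carryover between sessions; both should be stated. The simulations above used normal scores without diagnostic groups, so they do not test the egocentric count or the group terms.

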fMRI data analysis MRI images were preprocessed and analyzed through SPM8 (SPM8; Wellcome Trust Centre for Neuroimaging). Slice timing correction was performed for functional volumes. Functional volumes were realigned to the first volume in the experiment to correct for head motion, co-registered with the high-resolution sagittal images. The structural images were spatially normalized to a standard MNI template using the voxel-based morphometry toolbox (VBM8 <http://dbm.neuro.uni-jena.de/vbm>) and DARTEL high-dimensional warping and resampled to a 3x3x3 mm voxel size. Estimated deformation fields from warping were applied to normalize images to MNI space, and smoothed using a 5-mm FWHM Gaussian kernel. Motion scrubbing (removal of volumes) was performed based on a framewise displacement threshold of 0.3. The time course data for each voxel was band-pass filtered (0.01 to 0.10 Hz band) to capture the low-frequency spontaneous BOLD oscillations in resting state signals.

Task analysis

For the spatial navigation task, preprocessed MRI data were analyzed with the general linear model framework in SPM8. Two block regressors were modeled: allocentric and egocentric. The onsets and durations of blocks were convolved with a canonical hemodynamic response function (HRF) to create the block regressors, in addition to covariates of six image realignment parameters to reduce movement induced artifacts. In the first-level analysis for each participant, the parameter estimates of block regressors were computed at each voxel. Appropriate linear contrasts were applied to the parameter estimates to produce contrast images and statistical parametric maps (SPM t map). To evaluate activations associated with task, session, and group effects, we've

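### Resting-state volumes are described as removed for motion and then band-pass filtered, with no step to restore even sampling; this adds motion-dependent noise to the connectivity values.

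*Combined protocol and SAP*

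**What the plan says.** The fMRI data analysis section gives a single preprocessing account. After slice timing, realignment, normalisation and smoothing it says: "Motion scrubbing (removal of volumes) was performed based on a framewise displacement threshold of 0.3". No unit is given for 0.3, and no minimum number of retained volumes. The next sentence says that each voxel's time course "was band-pass filtered (0.01 to 0.10 Hz band) to capture the low-frequency spontaneous BOLD oscillations in resting state signals". The fMRI Scanning section gives a resting-state TR of 900 ms and a task TR of 1200 ms.

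The Resting state analysis section correlates the right superior parietal seed with every other voxel, and then correlates all pairs among 264 coordinate-based ROIs plus added medial temporal and subcortical ones. Seed maps go to second-level ANOVA and t-tests. Graph measures are computed from the edges that survive an FDR threshold.

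For the task, the Task analysis section says: "For the spatial navigation task, preprocessed MRI data were analyzed with the general linear model framework in SPM8". On how the regressors are built, it says: "The onsets and durations of blocks were convolved with a canonical hemodynamic response function (HRF) to create the block regressors". The only motion terms that it lists for this model are the six parameters from realignment, entered as covariates. Interpolation, indicator regressors for flagged volumes, matched deletion of design rows, and a comparison of motion by group or session are not mentioned anywhere.

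**The concern.** A band-pass filter with cut-offs in Hz assumes that consecutive samples are a fixed time apart, here 0.9 s. Deleting volumes joins points that were not adjacent, and the filter treats each join as one ordinary step. The filtered signal near a join is a mixture that never occurred in real time, and the effective pass-band shifts with the share deleted.

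The connectivity values are a planned Aim 2 outcome. If their noise depends on how much a participant moved, the group or session with more motion is measured less precisely. The plan would not show this, because it does not report volumes removed.

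The task model has a related exposure, but only conditionally. Its regressors are tied to clock time, so the plan needs to say whether task volumes were also deleted and, if so, how the design was kept in step.

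**Working it through.** The plan states no error rate or precision figure on this point, so there is nothing of its own to reproduce.

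**Inputs from the documents.** Resting TR 0.9 s; task TR 1.2 s; filter band 0.01 to 0.10 Hz; scrubbing by removal at framewise displacement 0.3.

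**Assumptions (not in the documents).** 533 resting volumes (533 × 0.9 s = 480 s, about 8 minutes); 0 to 30% of volumes removed; a Butterworth filter; motion spikes added to the flagged volumes except where stated.

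**Step 1: shift of the pass-band.** If a share f of volumes is deleted and the remainder is treated as 0.9 s apart, the average real cut-off is the nominal cut-off × (1 − f).
- f = 10%: 0.01 × 0.9 = 0.009 Hz and 0.10 × 0.9 = 0.09 Hz.
- f = 20%: 0.008 and 0.08 Hz.
- f = 30%: 0.007 and 0.07 Hz.

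**Step 2: error in connectivity.** For each simulated pair of series, z = arctanh(r), and the error is RMS = √mean[(z − z_intact)²], where z_intact comes from the filtered, complete, artefact-free series.

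| Removed | Remove, then filter | Interpolate, filter, then censor | Reduction |
|---|---|---|---|
| 10% | about 0.045 | about 0.034 | 1 − 0.034/0.045 = 24% |
| 30% | about 0.09 | about 0.066 | 1 − 0.066/0.09 = 27% |

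The remaining 0.034 and 0.066 come from data that were lost, which no ordering recovers. Only the difference between the columns is due to the order.

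**Step 3: bias and spread.** In a separate simulation run with spikes, mean z was 0.352 with nothing removed.

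| Removed | Remove, then filter: mean (SD) | Interpolate, filter, censor: mean (SD) | Filter with spikes in, then censor: mean (SD) |
|---|---|---|---|
| 0% | 0.352 (0.124) | 0.352 (0.124) | 0.352 (0.124) |
| 10% | 0.356 (0.123) | 0.354 (0.117) | 0.465 (0.121) |
| 20% | 0.342 (0.140) | 0.336 (0.129) | 0.541 (0.122) |
| 30% | 0.339 (0.146) | 0.338 (0.127) | 0.621 (0.124) |

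The first two orders agree in mean to within 0.006. At 30% removed, the variance relative to no removal is (0.146/0.124)² = 1.39 with removal first and (0.127/0.124)² = 1.05 with interpolation. At 10% the overall SD is barely affected. Filtering with the spikes left in is clearly biased upward.

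**Step 4: task, conditional only.** If task volumes were deleted and the regressors left unchanged, each deletion would move later data 1.2 s earlier relative to the design. With 400 volumes assumed and 5% removed, the cumulative shift by the end of the run is 400 × 0.05 × 1.2 s = 24 s. Across the assumed run lengths, block designs and removal patterns tried, the mean estimate of a true beta of 1.0 at 5% removed ranged from −0.15 to 0.89. With matching design rows dropped, which is equivalent to indicator regressors, it stayed at 0.99 to 1.02 for 0 to 20% removed.

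**The case against.** The strongest case on the other side is that this is a reporting gap. Sentence order need not be processing order, and interpolation may have been done without being mentioned. At modest scrubbing rates the resting-state penalty is small, and mean connectivity is not shifted.

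Much of that stands. The effect is on precision, and its size depends on a removal rate that the documents do not give. But the order as written is inferior to a cheap alternative. If the true order was the reverse, with filtering done while the contaminated volumes were still in the series, the result is worse (mean z 0.54 against 0.35 at 20%). Either way the plan needs the interpolation step.

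A reader might go further and infer that task betas were corrupted, so that a motion difference appears as an activation difference; one set of assumptions (1% against 5% of volumes removed, 30 s blocks) gives a 37% gap with no true difference. The documents do not support this. They never say that task runs were scrubbed, the filter sentence beside the scrubbing sentence is explicitly about resting-state signals, and the task model has its own stated motion control. Misalignment would also require the design rows to have been left unmatched, which is not stated either. Even then, a spurious contrast needs unequal removal: at 5% against 5% the simulated false-positive rate was 4 to 7%.

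**Conclusion.** The resting-state point holds: as described, removal precedes filtering and nothing restores even sampling. The consequence is extra noise in the seed and ROI-pair correlations that increases with motion. Interpolating first lowers the RMS error in Fisher z by roughly a quarter, with no material change in the mean. These figures are illustrative and rest on an assumed 533 volumes, assumed removal rates and a simulated artefact. They concern a single correlation; the effect on the graph measures was not simulated.

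The task point is a request for clarification. Unmatched removal would attenuate betas by an amount that depends on motion, mainly exposing the HC against MCI contrasts, which the plan labels exploratory. Active against sham is less exposed, because it is a within-person comparison with randomised order. No attenuation figure or activation gap should be attributed to the plan. The behavioural analyses of Aim 1 are unaffected.

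**What to change.** **Resting state.** Flag high-motion volumes, interpolate across them, filter the full-length series, then exclude the flagged volumes when computing seed and ROI correlations. Do not filter with the contaminated volumes left in.

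**Task.** State whether task runs were scrubbed. If they were, keep every volume and add one indicator regressor per flagged volume, or drop the matching design and realignment-parameter rows. If they were not, one sentence saying so closes the point.

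**Reporting.** Give the unit of the 0.3 threshold and a minimum amount of retained data, and report volumes removed by group and session.

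**Cost.** Resting preprocessing must be re-run, with the seed maps and graph analyses that depend on it. If task runs were scrubbed without matching rows, the first-level models, masks and extracted betas must be redone as well. Each flagged task volume costs one degree of freedom, which removal would cost anyway. No new data are needed.
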